10.0 Criteria for Response and Toxicity

10.1 Definition of primary endpoint:

- 10.1.1 Time to cognitive failure on any of the 6 primary variables from the pre-specified cognitive tests (HVLT-R total recall, HVLT-R delayed recall, HVLT-R delayed recognition, TMT Part A or Part B, COWA) with failure defined as a decline that meets or exceeds the reliable change index (RCI) for each cognitive test variable. A cumulative incidence approach will be used to estimate median time to cognitive failure in order to account for the competing risks of disease progression and death. Patients experiencing disease progression or patients that died prior to experiencing cognitive failure will be considered as having had a competing event. Progressive disease frequently causes cognitive decline, and the goal of this study is to assess the impact of the radiation treatment itself on cognitive decline.
- 10.2 Definitions of secondary endpoints:
 - 10.2.1 Local control and distant control in the brain will be measured by contrast-enhanced brain MRI scan using Response Assessment in Neuro-Oncology (RANO)Criteria, as follows [50].
 - 10.2.1.1 Complete Response (CR): Requires all of the following 1) complete disappearance of all enhancing measurable and non-measurable disease sustained for a minimum of 4 weeks; 2) no new lesions; 3) stable or improving nonenhancing (T2/FLAIR) lesions; 4) patients must be off corticosteroids (or on physiologic replacement doses only); and 5) stable or improved clinically.
 - 10.2.1.2 Partial Response (PR): Requires all of the following: 1) ≥50% decrease compared with baseline in the sum of products of perpendicular diameters of all measurable enhancing lesions sustained for at least 4 weeks; 2) no progression of non-measurable disease; 3) no new lesions; 4) stable or improved non-enhancing (T2/FLAIR) lesions on the same

or lower dose of corticosteroids compared with the baseline scan; 5) stable or improved clinically.

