12.0 Statistical Considerations

- 12.1 Randomization procedure: A stratified block randomization procedure will be used. Randomization will be performed using CORe. The randomization strata are as defined above in section 7.0, and the block size will be 6. Patients who withdraw from the study after randomization, but prior to receiving treatment will be considered a cancel and replaced.
- 12.2 Sample size: With IMRT the cognitive function failure rate at 4 months is 45%, based off of comparative analyses of the cognitive failure rate of RTOG 0614 and compared to the cognitive impairment seen on RTOG 0525; we hope to demonstrate that IMPT can achieve a cognitive function failure rate at 4 months of only 30%. We assume the time to cognitive failure in each treatment arm follows an exponential distribution. A cognitive failure rate of 45% at 4 months then implies a median time to cognitive failure of 4.6 months, while a cognitive failure rate of 30% at 4 months implies a median time to cognitive failure to cognitive failure of 7.8 months.

We will use a 1-sided significance level of 0.20 as suggested by Rubinstein et al. [51]for phase II screening trials. We expect to enroll 2 patients per month, and we will randomize 60 evaluable patients (30 to each treatment arm). We will have 80% power to detect an improvement in cognitive failure at 4 months from 45% in the IMRT arm to 30% in the IMPT arm. We expect to observe 43 events, and the analysis will be performed once we have observed these events. We define evaluable patients as those who have received the assigned treatment *and* completed baseline and at least one follow-up neurocognitive testing. We expect we will need an over accrual of 33% to account for those patients not evaluable. Therefore the target total enrollment sample size is 90 patients to accrue a total of 60 evaluable patients. We expect to observe 43 events, and we expect the trial to take 41 months to observe these events.

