- 12.3 Primary Analysis: The analysis will be performed on the intention-to-treat principle. Considering those patients who are not evaluable as treatment failures. We will use the methods of Gooley et al. [52]to estimate the cumulative incidence of cognitive failure in each treatment arm, considering progressive disease and death before cognitive failure as competing events. We will estimate the cumulative incidence of cognitive failure at 4 months with 95% confidence intervals. We will use the methods of Fine and Gray [53]to test for a difference between treatment arms with respect to the cumulative incidence of cognitive failure, considering progressive disease and death before and death before and death before cognitive failure as competing events. We will use the methods of Fine and Gray [53]to test for a difference between treatment arms with respect to the cumulative incidence of cognitive failure, considering progressive disease and death before cognitive failure as competing events. Our model will include treatment arm and the stratification factors used at randomization.
- 12.4 Secondary Analysis:

We will repeat the primary analysis on only those patients considered evaluable. All the secondary analyses described below will be performed using all patients as well as using only evaluable patients. We will estimate the cumulative incidence of local failure using the methods of Gooley et al. considering death as a competing event. We will model the time to local failure using the methods of Fine and Gray to test for differences between treatment arms, considering death as a competing event. Our model will include treatment arm and the stratification factors used at randomization, as well as selected dosimetric parameters. We will similarly analyze time to distant failure.

We will use the product limit estimator of Kaplan and Meier [54] to estimate overall survival stratified by treatment arm. We will also use Cox proportional hazards regression [55] to model overall survival as a function of treatment arm and the stratification factors used at randomization.

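### Section 12.2's 80% power is a log-rank figure for 60 evaluable patients; it does not carry over to the primary ITT Fine-Gray test, and the 43-event trigger has no calendar limit

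*Combined protocol and SAP*

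**What the plan says.** Section 12.2 assumes exponential times to cognitive failure, with 45% (IMRT) and 30% (IMPT) failing by 4 months, a one-sided 0.20 level and 80% power. On accrual it says "We expect to enroll 2 patients per month, and we will randomize 60 evaluable patients", and then "Therefore the target total enrollment sample size is 90 patients to accrue a total of 60 evaluable patients". An evaluable patient has received the assigned treatment and "completed baseline and at least one follow-up neurocognitive testing". The timing of the analysis is event-driven: "the analysis will be performed once we have observed these events". The expected number and date are given as "We expect to observe 43 events, and we expect the trial to take 41 months to observe these events". No rate of progression or death appears in the section.

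The endpoint in section 10.1.1 uses cumulative incidence "in order to account for the competing risks of disease progression and death". Section 12.3 makes the primary analysis intention-to-treat, "Considering those patients who are not evaluable as treatment failures", and tests the arms by Fine-Gray, "considering progressive disease and death before cognitive failure as competing events". The analysis of evaluable patients, which is the set that 12.2 sizes, is secondary (section 12.4). Cognitive testing ends two years after radiation (section 9.2).

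**The concern.** The power calculation and the primary test differ in three ways: the analysis set, the treatment of competing events, and the imputed failures. Imputed failures fall on both arms alike and dilute the difference. Competing events reduce the number of cognitive failures and, if 45% and 30% are net rates, also pull the subdistribution hazard ratio toward 1.

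In a one-sided 0.20 screening trial, a negative result is informative only if the power is close to what was stated. The trigger matters as well. Because testing stops at 24 months, failures may never reach 43, and the plan gives no rule for that case.

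**Working it through.** **1. Reproducing the plan's figures.** Inputs are from section 12.2.
- Hazards: -ln(0.55)/4 = 0.1495 and -ln(0.70)/4 = 0.0892 per month. HR = 0.597, ln HR = -0.516.
- Events: 4(0.842 + 0.842)²/0.516² = 42.5, so 43.
- Power at 43: Φ(√43/2 × 0.516 - 0.842) = 80.3%.
- Enrolment: 60/(1 - 0.33) = 90.

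These are correct for a log-rank test with a single event type.

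**2. The 41 months.** The expected count is the failure probability integrated over uniform entry, with follow-up capped at 24 months from enrolment (assumed).
- 2 enrolled per month, 60 of 90 evaluable (1.33 evaluable per month), no competing events: 42.1 failures at month 41 (42.9 without the cap).
- 2 evaluable per month, no competing events: 53.5 at month 41.
- 2 evaluable per month, deaths at the two-year survival of 27.2% cited in section 4.0 (hazard -ln(0.272)/24 = 0.0542 per month), starting at month 2 to 2.3: 42.9 to 43.3 at month 41. This needs 2 × 90/60 = 3 enrolled per month.

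Both the first and the third reading give 41 months.

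**3. Imputation alone.** With one third imputed, the 4-month rates become 1/3 + 2/3 × 0.45 = 63% and 1/3 + 2/3 × 0.30 = 53%. One third is an upper bound, because section 12.1 replaces pre-treatment withdrawals and section 7.2 removes patients whose insurer refuses. Section 12.3 gives no date for an imputed failure. Two dates were tried: enrolment, and 2.5 months (30 fractions plus about 4 weeks to the first test).

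**4. Adding deaths.** An evaluable patient must survive to the first follow-up test, so the death hazard m = 0.0542 starts at s = 3 months. Progression is ignored. For cognitive hazard l, cumulative incidence at t > s is 1 - exp(-l·s) + exp(-l·s) × l/(l+m) × [1 - exp(-(l+m)(t-s))]. At 1.33 evaluable per month this gives 35.7 failures at month 41, and 45.3 of 60 after full follow-up.

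Power was simulated for the one-sided 0.20 log-rank on subdistribution times, without strata. In the trigger runs 90 patients enter over 45 months, and the test is done at 43 observed failures or at month 70.5 (45 + 1.5 + 24). Simulation error is about 1 point.

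| Scenario | Power |
|---|---|
| Evaluable, no competing events | about 80% |
| ITT, one third imputed at enrolment | about 71% |
| ITT, one third imputed at 2.5 months | about 77% |
| ITT, one third imputed, counted toward the 43 | about 56% |
| ITT, 10-20% imputed | about 73-78% |
| Deaths from month 3, evaluable | about 72-75% |
| Deaths from month 3, ITT, one third imputed (enrolment / 2.5 months) | about 64% / 71% |

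In the runs with deaths, 43 failures were reached about 80% of the time, and the mean analysis month was about 52.

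**5. Faster competing rates (assumed).** Median times to progression or death of 12, 8 and 6 months, from month 3 with full follow-up, give 44.8, 41.3 and 38.5 expected failures in 60 patients. The chance of reaching 43 is 76%, 37% and 14%. Power is 75%, 74% and 72% in evaluable patients, and 66%, 64% and 62% in ITT with one third imputed at enrolment.

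**6. The favourable reading.** If 0.597 is the subdistribution hazard ratio and about 43 to 45 failures occur, power is about 80% in evaluable patients. In ITT it is 78-79% with 10% imputed and 80.5-81% with 5% imputed.

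**The case against.** The strongest reply is that nothing in 12.2 is miscalculated, and that its 45% and 30% may already be cumulative incidences. Sections 10.1.1 and 12.3 report the endpoint as a cumulative incidence, so this reading is plausible. Step 6 shows that power then stays near 80%, provided few patients are imputed. It follows that not every ITT scenario falls below 80%. What stands against it is that 12.2 does not say so, and does not give the imputed share on which the result depends.

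A reader might infer from the 41 months that competing events were ignored. The documents do not support that: step 2 shows that the same duration arises with deaths included, if 2 per month counts evaluable patients.

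A reader might also infer that true power is near 50%. That figure needs a 6-month competing median running from enrolment together with the full one third imputed. Deaths before the first test make a patient non-evaluable, so running the death hazard from enrolment in the 60 evaluable patients contradicts 12.2's own definition.

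Finally, the imputation rule is a sentence fragment that speaks of treatment failures and gives no date, so its effect is uncertain. That is true, and it is itself a reason to specify it. Annual DSMB review (section 14.3) provides oversight but does not set a rule for when to analyse.

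**Conclusion.** The point holds as a mismatch between 12.2 and 12.3, not as an arithmetic error. The 80% is not shown to be a property of the primary test. With the plan's own one-third non-evaluable share and no competing events, ITT power is about 71% to 77%, or about 56% if imputed failures count toward the trigger. With deaths alone added from month 3 it is about 64% to 71%, and faster competing rates lower it further.

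The imputation result needs no outside rate, only an assumed share and date. Every result with competing events rests on assumed hazards, because the documents give a survival figure for a cited trial but no progression rate. The absence of a rule if 43 failures are not reached does not depend on any of these assumptions.

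**What to change.** In section 12.2:
- State the assumed competing-event rate, and whether 45% and 30% are net rates or cumulative incidences.
- Say whether 2 per month counts enrolled or evaluable patients.
- Restate power, expected events and duration for the ITT Fine-Gray test, with the assumed imputed share, the date given to an imputed failure, and whether patients replaced under 12.1 stay in the set. Give the same figures for the evaluable set.
- Say that the 43 events are observed cognitive failures, not imputed ones.
- Add a calendar limit, for example 43 observed failures or the end of the planned 24-month testing of the last patient, whichever comes first.

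The cost is wording, one rerun of the power calculation, a lower stated power and a longer stated duration. At 2 enrolled per month the outer limit would be about month 70 (45 of accrual, about 1.5 of radiation, 24 of testing). No extra patients are needed.

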10.2.1.3 Progressive Disease (PD): Defined as any of the following 1) \geq 25% increase in the sum of the products of perpendicular diameters of enhancing lesions compared with the smallest tumor measurement obtained either at baseline (if no decrease) or best response, on stable or increasing dose of corticosteroids; 2) significant increase in T2/FLAIR nonenhancing lesion on stable or increasing doses of corticosteroids compared with baseline or best response not caused by comorbid events (i.e. radiation therapy. demvelination, ischemic injury postoperative changes); 3) any new lesion; 4) clear clinical deterioration not attributable to other causes apart from tumor (i.e. seizures, medication adverse effects, complications of therapy, cerebrovascular events, infection, or decrease in corticosteroid dose); 5) failure to return for evaluation due to death or deteriorating condition; 6) clear progression of non-measurable disease.

When making the diagnosis of progressive disease it is import to recognize the possibility of pseudo-progression, especially if the patient is clinically stable. In those situations, treatment should continue and status of local control should be evaluated with a repeat interval scan. If the subsequent scan confirms progression then the date of progression should be backdated to the original scan suggesting progression.

- 10.2.1.4 Stable Disease (SD): Requires all of the following 1) does not qualify for complete response, partial response, or progression; 2) stable FLAIR/T2 lesions on corticosteroid dose no greater than at baseline; 3) clinical status stable.
- 10.2.1.5 For local control, PD is considered local failure, or stable disease with deterioration of the neurological examination with a grade III or worse toxicity on the CTCAE v.4.0 scale (see Appendix). All others (CR, PR, asymptomatic SD) are deemed success.
- 10.2.2 Overall survival will be measured from registration until death. After 2 years of follow-up event monitoring will be used.
 - 10.2.2.1 Patients with unknown vital status will be censored at the date of last visit or MRI scan.
- 10.2.3 Quality of life will be measured at each two month interval follow up visit out to two years using the EORTC QLQ C30/BN20 and the MD Anderson Symptom Inventory Brain Tumor (MDASI-BT).

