11.0 Criteria for Removal from the Study

- 11.1 Analysis will be by intention-to-treat and those patients who withdraw from the study after randomization, but prior to receiving treatment will be tracked to ensure there is no bias introduced into the study.
- 11.2 Patients who do not complete the assigned treatment will be recorded and followed. These patients can be treated by best medical therapy as per the judgment of the treating physicians.

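### Section 12.3 gives patients who progress or die before the first follow-up test two event codes and leaves other non-evaluable patients without an event date, and the 80% power in 12.2 belongs to the evaluable-patient analysis that 12.4 makes secondary

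*Combined protocol and SAP*

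**What the plan says.** **Primary analysis (12.3).** "The analysis will be performed on the intention-to-treat principle. Considering those patients who are not evaluable as treatment failures". The same section estimates cumulative incidence and fits a Fine-Gray model, with progression and death before cognitive failure as competing events.

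**Endpoint (10.1.1).** Cognitive failure requires a measured change: "failure defined as a decline that meets or exceeds the reliable change index (RCI) for each cognitive test variable". The competing-event rule has no exception for non-evaluable patients: "Patients experiencing disease progression or patients that died prior to experiencing cognitive failure will be considered as having had a competing event". The reason given is that "the goal of this study is to assess the impact of the radiation treatment itself on cognitive decline".

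**Progression (10.2.1.3).** One criterion is "failure to return for evaluation due to death or deteriorating condition".

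**Evaluable (12.2).** The patient was given the allocated treatment and "completed baseline and at least one follow-up neurocognitive testing". Power is tied to this group: "the target total enrollment sample size is 90 patients to accrue a total of 60 evaluable patients". The analysis is triggered by 43 events, expected at 41 months.

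**Secondary analyses (12.4).** These include a repeat on evaluable patients only, and as-treated versions of nearly all analyses.

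**Analysis set.** Section 11.1 declares intention-to-treat and adds that "those patients who withdraw from the study after randomization, but prior to receiving treatment will be tracked to ensure there is no bias" is introduced. Section 7.2 takes patients off study after randomization if insurance refuses the allocated arm. Section 12.1 cancels and replaces those who withdraw before treatment.

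**The concern.** A Fine-Gray analysis needs one event type and one time for each patient. For the non-evaluable patients, a planned third of enrolment, the plan gives either two types or no time. Someone has to choose when the analysis is programmed, possibly with outcome data in view, and the choice affects the primary test.

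The meaning of the endpoint is also at stake. Section 10.1.1 treats progression as competing in order to isolate the effect of radiation. Scoring an early progressor as a cognitive failure puts tumour progression back into the endpoint.

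Finally, a reader of 12.2 would take 80% as the power of the primary test. It is the power of a different analysis.

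**Working it through.** **1. Inputs, all from 12.2.** One-sided alpha 0.20; 4-month failure 45% (IMRT) and 30% (IMPT); exponential times; 43 events; 60 evaluable of 90 enrolled; 2 patients per month; 41 months.

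**2. Reproducing the plan's figures.**
- Hazards: −ln(0.55)/4 = 0.1495 and −ln(0.70)/4 = 0.0892 per month, so HR = 0.597 and |ln HR| = 0.5165.
- Schoenfeld power at 43 events: Φ(√(43/4) × 0.5165 − 0.842) = Φ(0.852) = 0.803.
- Enrolment: 60/(1 − 0.33) ≈ 90.
- Expected events at month t with steady accrual of n per arm: n[1 − (1 − e^(−λt))/(λt)]. Evaluable patients arrive at 2 × 60/90 = 4/3 per month. At t = 41, n = 27.3 per arm, giving 22.9 + 20.1 ≈ 42.9 events. In simulation the 43rd observed failure falls at about month 41 to 42.

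The 41 months fits only this count. Sixty patients at 2 per month would reach 43 events near month 30. If imputed failures counted towards the 43, the trigger would come at about month 27 to 28.5. The formula contains no competing-event rate.

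**3. The rules side by side.**

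| Patient | Non-evaluable clause of 12.3 | 10.1.1 and the rest of 12.3 | Date for an imputed failure |
|---|---|---|---|
| Progresses or dies before first follow-up test | Failure | Competing event | None given |
| Does not return because of death or deterioration | Failure | Progression (10.2.1.3), so competing | None given |
| Other patient with no usable follow-up test | Failure | No measured decline | None given |
| Usable tests, but not given the allocated treatment | Failure | Own test result | None given |
| Removed (7.2) or cancelled (12.1) | Failure, if in the set | Not stated | None given |

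This reads treatment failure, which is undefined, as cognitive failure, the only failure that 12.3 models. Patients who progress after completing a follow-up test on the allocated treatment are evaluable and unaffected.

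**4. Failure imputation alone, arms balanced.** With 15 non-evaluable per arm, the 4-month rates become 1/3 + 2/3 × 0.45 = 63.3% and 1/3 + 2/3 × 0.30 = 53.3%. Simulated power, with imputed failures dated 0, 2 or 4 months, is 74%, 77% and 79% at the 43rd observed failure, and 77 to 83% if all 90 are enrolled first. Type I error is 16 to 20%. The cost is small.

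**5. Event-code choice, no later competing events in evaluable patients.** Assumptions: one third non-evaluable with the same chance in each arm; those without early progression or death scored as failures at 0, 2 or 4 months; block size 6; 24-month cap; unadjusted log-rank with competing cases kept in the risk set to administrative censoring (the Fine-Gray score test); analysis at the 43rd observed failure; 8,000 to 12,000 replicates.

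| Early progressions or deaths among 90 (assumed) | Power if coded failure (date 0 / 4 months) | Power if coded competing (0 / 4 months) | Gap, points |
|---|---|---|---|
| 5 | 70.4 / 77.7% | 63.3 / 70.0% | 7.1 / 7.7 |
| 10 | 70.4 / 77.7% | 59.7 / 65.0% | 10.7 / 12.7 |
| 20 | 70.4 / 77.7% | 55.7 / 58.7% | 14.7 / 19.0 |

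A separate run of the same set-up gave a gap of 7 to 20 points. False positives stay at 20 to 21% under either code.

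**6. With later competing events in evaluable patients.** The documents give no rate for these. The 27.2% two-year survival in section 4.0 implies −ln(0.272)/24 = 0.054 deaths per month if exponential, before counting progression. At an assumed 0.03 to 0.06 per month, with the plan's rates taken as cause-specific, the gap falls to roughly 2 to 13 points. At 0.06, power is about 57 to 65% even when every non-evaluable patient is scored a failure.

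**The case against.** **The rules can be read together.** The specific competing-event rule could govern progression and death, leaving the non-evaluable clause to cover the rest; 10.2.1.3 points that way. This is sensible, and the fix adopts it, but the plan does not say so, and it still dates no imputed failure. The 4-month cumulative incidence needs only failure by month 4, but it too depends on the event code.

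**Most of the power loss has another source.** A reader might infer that the coding conflict by itself costs 7 to 20 points. That range requires evaluable patients never to progress or die first, which does not fit an endpoint built around those events. Once they can, the gap shrinks and most of the shortfall comes from 12.2 omitting competing events. This stands.

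**Imputation and imbalance.** A reader might infer that scoring non-evaluable patients as failures wrecks power or biases the test. Balanced imputation does neither (step 4). An assumed 12 IMRT / 18 IMPT split would cut power to 41 to 69%, and 17/13 with no true effect would give 23 to 33% false positives. The documents give no rate by arm and predict no imbalance, so these figures are illustration only.

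**Secondary analyses help.** The evaluable-only and as-treated analyses are planned and will be informative. They do not settle how the primary analysis is coded.

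**Censoring is no better.** Failure imputation may be deliberate, and censoring assumes missingness at random, which is doubtful here. The documents do not show either to be right.

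**Conclusion.** The concern holds and should be settled before the arms are compared. Two stated rules conflict for the primary endpoint, other imputed failures have no date, and patients with usable tests who did not receive the allocated treatment have their results overridden. The 12.2 figures are correct for evaluable patients, and a reader should not infer an arithmetic error in the sample size. The gap is that the primary analysis has no stated power and competing events are left out.

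The size rests on assumptions: balanced arms, 5 to 20 early progressions or deaths among 90, and imputed dates of 0 to 4 months. The event-code choice is worth about 7 to 20 points of power with no later competing events, and roughly 2 to 13 points at 0.03 to 0.06 per month. At those hazards power is below 80% under either code, mainly because of the competing events themselves.

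**What to change.** In 12.3, analyse randomised patients in their allocated arm under one hierarchy:

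1. An observed RCI decline is the event.
2. Progression or death before a decline, including before the first follow-up test, is a competing event, as in 10.1.1.
3. Patients with usable tests count on their own results, whatever treatment they received.
4. For patients with no usable test and no progression or death, either keep the failure rule with a stated date or censor them, with the other as a labelled sensitivity analysis. The choice is the sponsor's.

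In 12.2, state that the 43 events are observed RCI failures and that the 80% applies to the evaluable-patient analysis. Restate power for the primary analysis with an explicit competing-event rate, including in evaluable patients. Say whether patients removed under 7.2 or cancelled under 12.1 are in the 12.3 set, consistent with 11.1.

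The cost is SAP wording, one power rerun and a lower stated power. For scale, the hierarchy with censoring under item 4 gives 80%, 71%, 66% and 59% for an assumed 0, 5, 10 and 20 early progressions or deaths among 90 with no later competing events, and about 65%, 64%, 60% and 56% at 0.06 per month. That loss follows from the competing-event rule already in 10.1.1; the present 80% does not show it.
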